### 8.2 Secondary Efficacy Endpoints

#### 8.2.1 Success Rates in IGA (Revised Definition) and EASI

The success rate in achieving an IGA score of 0 or 1 (revised definition from primary efficacy endpoint) by Week 4 and the success rate in EASI 75, EASI 90, and EASI 50 by Week 4 will be analyzed in the same manner as the primary endpoint in [Section 8.1.1](#)

For IGA, subjects who achieve a score of 0 or 1 in IGA will be handled as responders and subjects who do not achieve a score 0 or 1 in IGA will be handled as non-responders. Subjects with missing IGA data will be handled as non-responders.

EASI 75 will be set as the important secondary endpoint, and subjects whose percentage change in their total EASI score from baseline decreases by  $\geq 75\%$  will be handled as responders and subjects whose percentage change from baseline does not decrease by  $\geq 75\%$  will be handled as non-responders. Subjects with missing EASI 75 data will be handled as non-responders. EASI 90 and EASI 50 will be analyzed in the same manner. Similarities with the primary endpoint results will be assessed using response rates in EASI (EASI 75, EASI 90, and EASI 50).

### **8.2.2 Change From Baseline Through Week 4 in the IGA Score**

Based on the OC data set, change from baseline (Week 1, Week 2, and Week 4) will be analyzed using a mixed-model repeated measure (MMRM) with treatment (0.3% OPA-15406 or 1% OPA-15406 and vehicle), timepoint, interaction between the treatment and timepoint as factors and baseline values as covariates. An unstructured error covariance matrix will be used and Kenward-Roger method will be used to calculate the degree of freedom. If the MMRM procedure fails to converge under unstructured covariance structure, the following structure will be used in the order of 1) heterogeneous toeplitz, 2) heterogeneous autoregressive of order 1, and 3) heterogeneous compound symmetry, and the first error covariance structure converging will be used. The MMRM analysis with the structured error covariance matrix will use a sandwich estimator. The least square mean will be calculated by treatment group and timepoint.

The SAS code for MMRM analysis is as follows:

```
proc mixed method = reml ;  
  class Treatment Visit Subject ;  
  model Change = Treatment Visit Treatment*Visit Baseline / s ddfm = kr ;  
  repeated Visit / type = un sub = Subject ;  
  lsmeans Treatment*Visit / pdiff cl alpha = 0.05 ;  
run;
```

“Baseline” is baseline IGA data. “Visit” includes data at Weeks 1, 2, and 4.

The SAS code used in the case of convergence failure is as follows: (Specify *type* = *TOEPL* for heterogeneous toeplitz, *type* = *ARH(1)* for heterogeneous autoregressive of order 1, and *type* = *CSH* for heterogeneous compound symmetry.)

```
proc mixed method = reml empirical ;  
  class Treatment Visit Subject ;  
  model Change = Treatment Visit Treatment*Visit Baseline / s ;  
  repeated Visit / type = TOEPL sub = Subject ;  
  lsmeans Treatment*Visit / pdiff cl alpha = 0.05 ;  
run;
```

Based on the OC and LOCF data sets, change from baseline at each timepoint will be analyzed using an ANCOVA model with treatment (0.3% OPA-15406 or 1% OPA-15406 and vehicle) as factors and baseline IGA scores as covariates. The least square mean will be calculated at each timepoint (Weeks 1, 2, and 4) for each treatment group. Also, the difference in the least square mean between the vehicle group and each OPA-15406 group will be calculated along with its two-sided 95% confidence interval and p value. Based on the OC and LOCF data sets, the descriptive statistics will be calculated for measured values and changes from the baseline at each timepoint by treatment group.

A graph will be created for the least square mean and standard deviation for the change from baseline in IGA calculated by MMRM for each treatment group.

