7.4.2 Secondary Endpoint Analysis

- The success rate in IGA achieving a score of 0 or 1 at Week 4 and the success rate in EASI 75, EASI 90, and EASI 50 at Week 4

The secondary endpoint will be analyzed in the same manner as the primary endpoint.

For IGA, subjects who achieve a score of 0 or 1 in IGA will be handled as responders and subjects who do not achieve a score 0 or 1 in IGA will be handled as non-responders.

Subjects with missing IGA data will be handled as non-responders.

EASI 75 will be set as the important secondary endpoint, and subjects whose percentage change in their total EASI score from baseline decreases by $\geq 75\%$ will be handled as responders and subjects whose percentage change from baseline does not decrease by $\geq 75\%$ will be handled as non-responders. Subjects with missing EASI 75 data will be handled as non-responders. EASI 90 and EASI 50 will be analyzed in the same manner. Similarities with the primary endpoint results will be assessed using the response rates in EASI (EASI 75, EASI 90, and EASI 50).

- Change from baseline at Week 4 in the IGA score; the total EASI score; each EASI clinical sign score; VRS for pruritus (including Day 7); the total POEM score; and the total affected BSA (%).

Based on the OC data set, change from baseline (Week 1, Week 2, and Week 4) will be analyzed using a mixed model repeated measure (MMRM) with treatment (0.3% OPA-15406 or 1% OPA-15406, and vehicle), timepoint, interaction between the treatment and timepoint as factors and baseline values as covariates. An unstructured error covariance matrix will be used and Kenward-Roger method will be used to calculate the degree of freedom. If the MMRM procedure fails to converge under unstructured covariance structure, the following structure will be used in the order of 1) heterogeneous toeplitz, 2) heterogeneous autoregressive of order 1, and 3) heterogeneous compound symmetry, and the first error covariance structure converging will be used. The MMRM analysis with the structured error covariance matrix will use a sandwich estimator. The least square mean will be calculated by treatment group and timepoint.

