### **8.2.4 Change From Baseline Through Week 4 in the Total EASI Score and Each EASI Clinical Sign Score**

Based on the OC and LOCF data sets, the analysis will be performed in the same manner as for the change from baseline in IGA scores. In addition to clinical signs (erythema, infiltration/papule, excoriation, and lichenification), scores on body regions (face, neck, and head; upper limbs; trunk; and lower limbs) will also be analyzed in the same manner. For EASI, the percentage change will also be analyzed. A graph will be created for the least square mean and standard deviation for the change from baseline in the total EASI score calculated by MMRM for each treatment group.

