### **8.2.5 Change From Baseline Through Day 8 in VRS for Pruritus**

Based on the OC data set, the analysis will be performed in the same manner as for the change from baseline in IGA scores. Timepoints will include baseline through Day 8.

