### **8.2.6 Change From Baseline Through Week 4 in VRS for Pruritus**

Based on the OC and LOCF data sets, the analysis will be performed in the same manner as for the change from baseline in IGA scores. Timepoints will include baseline, Weeks 1, 2, and 4.

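### The MMRM for the continuous secondary endpoints fits one baseline slope for all visits; adding a baseline-by-visit term would guard the Week 4 (and VRS Day 8) contrasts against an avoidable loss of precision at almost no cost

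*SAP*

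**What the plan says.** Protocol 7.4.2 analyses change from baseline at Weeks 1, 2 and 4 with an MMRM whose terms are treatment, "timepoint, interaction between the treatment and timepoint as factors and baseline values as covariates". It applies this model to IGA, total EASI, EASI sign scores, VRS, POEM and affected BSA, and names no other model for these endpoints.

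SAP 8.2.2 repeats the text and gives the code. The main block has "model Change = Treatment Visit Treatment*Visit Baseline / s ddfm = kr", with an unstructured covariance. The block for convergence failure has the same mean model, "model Change = Treatment Visit Treatment*Visit Baseline / s". Treatment-by-visit is the only interaction in either.

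SAP 8.2.2 also adds an ANCOVA at each timepoint, with treatment "as factors and baseline IGA scores as covariates". It reports the difference in least square means against vehicle, with its 95% confidence interval and p value.

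The template is carried over in SAP 8.2.4, where "the analysis will be performed in the same manner as for the change from baseline in IGA scores"; 8.2.5 to 8.2.8 do the same for VRS, POEM and BSA. For daily VRS the SAP adds "Timepoints will include baseline through Day 8", and for VRS by week "Timepoints will include baseline, Weeks 1, 2, and 4".

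**The concern.** The response is change from baseline. Its regression slope on baseline at visit t is (correlation of visit t with baseline) x (SD at t / SD at baseline) - 1. If the correlation with baseline weakens over time, that slope becomes steeper. A model with one slope settles on a weighted compromise. When residual variance grows over time, the compromise lies near the early visits, and Week 4, the visit that defines these endpoints, is under-adjusted.

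What is at stake is the precision of the Week 4 contrasts, and of the Day 8 contrast for VRS. The information that would recover it is already in the model. Validity is not the issue: with randomized arms and complete data the common-slope contrast remains consistent.

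**Working it through.** **The plan's own figure.** The only design calculation is 72 per group for the binary primary endpoint (36% against 12%, 90% power, two-sided 5%; SAP 4). It reproduces: 73 with a continuity correction, and Fisher's exact test has 90.7% power at 72. It says nothing about the continuous endpoints, so there is no stated precision to check.

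**Inputs from the documents.** Mean model and visits: SAP 8.2.2. Planned n of 80 per arm: SAP 4. Baseline IGA is 2 or 3 (SAP 3.3), so its SD is at most about 0.5. VRS is collected only at ages 7-14 (protocol 3.7.1.5), about half of each arm under the 1:1 age target.

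**Assumed inputs.** All slopes, residual SDs and correlations below, and the baseline SDs of EASI and VRS.

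**Formulas.** With complete data, the contrast at visit t is the difference in mean change minus slope x the difference in baseline means. The variance with a common slope b, relative to visit-specific slopes β_t, is therefore

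1 + (β_t - b)² × Var(baseline) / Var(residual at t).

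The common slope is the generalized least squares average b = (1'M⁻¹β)/(1'M⁻¹1). M is the covariance that the common-slope model itself fits (residual covariance plus the leftover baseline variation), solved by iteration. The SE ratio is the square root of the variance ratio.

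**Equal slopes.** β_t = b, so the ratio is 1 and the loss is 0% for every endpoint.

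**IGA, Week 4** (baseline SD 0.5; residual SDs 0.6/0.75/0.9; adjacent-visit residual correlation 0.5 or 0.7):
- Slopes -0.2/-0.3/-0.4: SE +0.3% to +0.4%.
- Slopes -0.1/-0.3/-0.5: +1.3% to +1.8%.
- Slopes 0/-0.3/-0.6, correlation 0.7: b = -0.092, so 1 + 0.508² × 0.25/0.81 = 1.080, SE +3.9% (+2.9% at correlation 0.5).

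**EASI, Week 4** (baseline SD 6; residual SDs between 3 and 6; same correlations):
- Slopes -0.4/-0.5/-0.6: +1.1% to +2.4%.
- Slopes -0.2/-0.4/-0.6, SDs 4/5/6, correlation 0.5: b = -0.307, so 1 + 0.293² × 36/36 = 1.086, SE +4.2%. With SDs 3/4/5 and correlation 0.7: b = -0.234, so 1 + 0.366² × 36/25 = 1.193, SE +9.2%.
- Slopes -0.2/-0.5/-0.8: +9% to +20%. The top value has b = -0.251, so 1 + 0.549² × 36/25 = 1.434, SE +19.7%.

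**VRS, Day 8** (Days 2 to 8):
- Baseline SD 0.7, residual SD 0.6, slopes drifting from -0.2 to -0.7: b = -0.45, so 1 + 0.25² × 0.49/0.36 = 1.085, SE +4.2%. Milder drifts give +0.7% to +1.5%.
- Pure AR(1) daily correlation of 0.85 with equal SDs: the Day 8 slope is 0.85⁷ - 1 = -0.679 and b = -0.251, so 1 + 0.428²/(1 - 0.85¹⁴) = 1.204, SE +9.7%. At 0.95 the variance ratio is 1.110, SE +5.4%.
- With 20% of the variance as measurement noise, the AR(1) excess falls to about 3% to 8% of the variance, or 1.4% to 3.8% of the SE.

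**Simulation check for Week 4** (three-arm REML MMRM, 80 per arm, 300 runs per scenario, with and without about 17% missing at random at Week 4). The model SE ratios, common slope over interaction, were 0.998-1.034 for IGA and 0.998-1.166 for EASI. When slopes are equal the added term costs 0.1-0.2% of the SE.

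POEM and BSA were not computed separately. The same formula applies, but the documents give no values for them.

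**The case against.** The strongest reply is that a single baseline covariate is a legitimate, parsimonious model, and that these endpoints support no confirmatory claim. The closed procedure covers only the two IGA success-rate comparisons, and no power is claimed for the continuous endpoints. That stands. It limits the weight of the point without removing it.

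A second reply is that the per-visit ANCOVA already delivers contrasts with visit-specific slopes, and that the SAP does not rank it below the MMRM. This also stands in part. However, protocol 7.4.2 names only the MMRM, and the SAP draws its least-square-mean graphs for IGA and EASI from it. The ANCOVA either ignores earlier visits of children who drop out (observed cases) or imputes by LOCF, so it does not fully replace the MMRM.

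Four stronger readings may tempt a reader. The documents do not support them:
- *Every continuous endpoint loses precision.* The loss is zero if slopes are equal, and nothing in the documents shows how they behave.
- *EASI, VRS, POEM and BSA would be adjusted for baseline IGA instead of their own baseline.* The IGA wording sits in the IGA section. Protocol 7.4.2 applies baseline values to all these endpoints together, so substituting each endpoint's own baseline is the natural reading.
- *Listing baseline as a VRS timepoint puts a zero-variance visit into the model and makes the covariance matrix singular.* SAP 8.2.2 limits the modelled visits to post-baseline weeks, and its template includes descriptive statistics of measured values, which a baseline entry fits.
- *The treatment contrasts are biased.* With complete data they are consistent. With dropout, the steeper EASI simulations under no effect gave mean estimates of 0.13-0.20 points, against 0.04-0.06 with the interaction (Monte Carlo standard error about 0.05). That is at most a hint of a small bias in extreme scenarios.

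**Conclusion.** The point holds as a minor efficiency improvement to supportive analyses. No baseline-by-visit term appears in either document. Where slopes differ between visits, the MMRM gives wider intervals at later visits than it needs to.

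The loss is small for IGA because baseline IGA takes only two values. It is uncertain for VRS: the upper end of its range needs a pure AR(1) process without measurement noise, and Day 8 concerns VRS alone. It can be material only for a widely ranging baseline such as EASI. All the sizes rest on assumed slopes, SDs and correlations and should be read as a range, not a prediction. The primary endpoint, the closed test and the sample size are untouched.

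**What to change.** Add Baseline*Visit to the MODEL statement in both SAP 8.2.2 code blocks, and add the baseline-by-timepoint interaction to the model text in protocol 7.4.2 and SAP 8.2.2. Sections 8.2.4 to 8.2.8 inherit it.

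The cost is 2 extra parameters for the three-visit models and 6 for the seven-day VRS model. If the term is not needed, it costs about 0.1-0.2% of the SE in the Week 4 models; the daily VRS model, with about half the children, was not simulated for this. No new data are required.

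Two clarifications can be made in the same edit: state that the covariate is the baseline value of the variable being analysed, and state in SAP 8.2.5 and 8.2.6 that only post-baseline timepoints are modelled.

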### List of Definitions of Terms

Term	Definition
Descriptive statistics	Number of subjects, mean, standard deviation, maximum, median, and minimum
Frequency distribution	Number and percentage of subjects

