### 8.1.1 Primary Efficacy Analysis

The efficacy of the 0.3% and 1% OPA-15406 groups will be demonstrated compared to the vehicle group based on the primary endpoint, the success rate in IGA at Week 4. Overall type I errors will be controlled using a closed testing procedure. First, the 1% OPA-15406 treatment group and the vehicle group will be compared. If significant at the two-sided significance level of 5%, the 0.3% OPA-15406 treatment group and the vehicle group will then be compared at the two-sided significance level of 5%. The Cochran-Mantel-Haenszel test will be conducted for comparison using the baseline IGA (2 or 3) and age (“2 to 6 years” or “7 to 14 years”) as a stratification factor. The difference in the success rate in IGA and its two-sided 95% confidence interval (common risk difference adjusted by Mantel Haenszel method and its two-sided 95% confidence interval) between the vehicle group and 0.3% or the 1% OPA-15406 group will be determined. Also, the two-sided 95% confidence interval of the success rate in IGA in each treatment group (based on Clopper-Pearson method) will be calculated. In addition, the success rate in IGA in each treatment group at Week 4 and its two-sided 95% confidence interval will be plotted and the dose-response relationship will be graphically assessed.

The SAS code for the Cochran-Mantel-Haenszel test and to determine the difference in the success rate and two-sided 95% confidence interval is as follows:

```
proc freq ;
  tables Agegroup*BaselineIGA*Treatment*Response / riskdiff(common) cmh ;
run;
```

A supplementary analysis will be performed using data which includes missing data imputed by Last Observation Carried Forward (LOCF) and Observed Cases (OC) data which does not include the imputed missing data in the same manner.

Data at Weeks 1 and 2 will also be analyzed in the same manner as the primary endpoint at Week 4.

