### **8.2.8 Change From Baseline Through Week 4 in the Total Affected BSA (%)**

Based on the OC and LOCF data sets, the analysis will be performed in the same manner as for the change from baseline in IGA scores.

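### The two MMRM figures pair an LS mean with a standard deviation instead of a measure of precision; the continuous secondary models also omit factors that stratify the primary CMH test

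*SAP*

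**What the plan says.** **Figures.** SAP 8.2.2 specifies for IGA: "A graph will be created for the least square mean and standard deviation for the change from baseline in IGA calculated by MMRM". SAP 8.2.4 specifies a graph of the "least square mean and standard deviation for the change from baseline in the total EASI score calculated by MMRM". These correspond to CF-2.1 and CF-2.2, the only MMRM figures in SAP Appendix 3, and neither title names an error bar. The model code in 8.2.2 requests "lsmeans Treatment*Visit / pdiff cl alpha = 0.05", which returns LS means with standard errors and 95% confidence limits. Elsewhere the SAP treats the SD as one of its descriptive statistics ("Number of subjects, mean, standard deviation, maximum, median, and minimum"), and 8.2.2 already tabulates those for measured values and changes by arm and timepoint. For the primary endpoint figure, SAP 8.1.1 gives each arm's success rate, and "its two-sided 95% confidence interval will be plotted and the dose-response relationship will be graphically assessed".

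**Model terms.** The primary CMH test is stratified by baseline IGA (2 or 3) and age group (2–6 or 7–14 years). The binary secondary endpoints inherit this: the success rates in EASI 75, "EASI 90, and EASI 50 by Week 4 will be analyzed in the same manner as the primary endpoint". The MMRM for the continuous endpoints contains treatment, visit, their interaction and a baseline covariate. The ANCOVA has treatment groups "as factors and baseline IGA scores as covariates". Protocol 7.4.2 gives the same MMRM terms.

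**Baseline covariate.** SAP 8.2.2 says the code variable Baseline holds baseline IGA. For the later continuous endpoints, "the analysis will be performed in the same manner as for the change from baseline in IGA scores" (8.2.8, with matching wording in 8.2.4 to 8.2.7).

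**The concern.** A reader of a longitudinal LS-mean plot takes the bars as the uncertainty of the plotted mean. SD bars do not carry that meaning, and they do not shrink as the sample grows. Even a clearly significant treatment difference would be drawn with heavily overlapping bars. The instruction is also incomplete: the LS-mean statement yields no SD, and the SAP does not say whether the raw or the model residual SD is meant, so the programmer would have to choose.

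On the models, the plan treats age group and baseline IGA as worth adjusting for in the primary analysis, the binary secondary analyses and the exploratory logistic regression, but not consistently in the continuous secondary models. The possible loss is some precision.

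On the baseline covariate, a literal reading of the later sections would adjust EASI, VRS, POEM and affected BSA for baseline IGA instead of for their own baseline.

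**Working it through.** **Inputs.** Planned n is 80 per arm (Protocol 7.1, SAP 4). Phase 2 discontinuations due to AEs were 1 subject (4.2%) on 0.3%, 1 (4.0%) on 1% and 4 (16.7%) on vehicle (Protocol 1.2.9), with denominators 24, 25 and 24 (Protocol 7.1). The documents give no SD for IGA or EASI change, but the ratios below do not need one.

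**The plan's own figure.** The stated need is 72 per group for 36% versus 12%, two-sided 5%, 90% power. The pooled formula gives 65 without and 73 with continuity correction; Fisher's exact test has power 0.907 at 72. The figure therefore reproduces with a corrected or exact method. The target of 80 is the n used here.

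**Step 1: bar width.** Treating the LS mean as a simple arm mean with the model SD, SE = SD/√n and the 95% half-width is 1.96 × SD/√n. Hence SD/SE = √n and SD/half-width = √n/1.96.

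| Case | n | SD/SE | SD/half-width |
|---|---|---|---|
| Complete data | 80 | 8.94 | 4.56 |
| 0.3% arm, 80 × (1 − 1/24) | 76.7 | 8.76 | 4.47 |
| 1% arm, 80 × (1 − 1/25) | 76.8 | 8.76 | 4.47 |
| Vehicle, 80 × (1 − 4/24) | 66.7 | 8.16 | 4.17 |
| Assumed 20% missing | 64 | 8.00 | 4.08 |

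In the MMRM, earlier visits recover some of the missing Week 4 information. For vehicle, SD/SE = 1/√[(1 − R²)/66.7 + R²/80]. With assumed R² of 0, 0.25, 0.5 and 0.64 this gives 8.16, 8.34, 8.53 and 8.64.

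**Step 2: how it would look.** A difference that just reaches two-sided 5% at 80 per arm is 1.96 × √(2/80) = 0.31 SD. Bars of ±1 SD around two means 0.31 SD apart overlap almost completely.

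**Step 3: which factor is missing where.**

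| Endpoint | Baseline covariate | CMH factor absent |
|---|---|---|
| IGA change | baseline IGA | age group |
| EASI, POEM, affected BSA | own baseline, as intended | age group and baseline IGA |
| VRS for pruritus | own baseline, as intended | baseline IGA |

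In the IGA models, baseline IGA takes only the values 2 and 3, so a linear covariate is equivalent to the stratum factor. VRS is collected only at ages 7–14, so age group is constant there.

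**Step 4: size of the precision gain.** As a first approximation, if the added factors explain a share R² of the residual variance, the SE is multiplied by √(1 − R²): 0.995, 0.975 and 0.949 at 1%, 5% and 10%. A simulated three-arm single-visit ANCOVA (own baseline in the model, 50:50 factors, 2,000 replicates) gives these changes in the mean SE of an active-versus-vehicle difference:

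| Factors across arms | Per arm | Factors added | R² 0 | 1% | 5% | 10% |
|---|---|---|---|---|---|---|
| Balanced | 80 | two | 0.0% | −0.5% | −2.6% | −5.2% |
| Balanced | 80 | one | 0.0% | −0.5% | −2.6% | −5.2% |
| Balanced | 40 | one | 0.0% | −0.5% | −2.6% | −5.3% |
| Random | 80 | two | +0.4% | −0.1% | −2.1% | −4.7% |
| Random | 80 | one | +0.2% | −0.3% | −2.3% | −4.9% |
| Random | 40 | one | +0.5% | −0.1% | −2.0% | −4.7% |

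The 40-per-arm rows represent VRS under the 1:1 age target. Both balance cases are shown because Protocol 3.6 specifies minimization but leaves the details to a separate specification.

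**Step 5: baseline covariate.** Protocol 7.4.2 speaks of baseline values in general, and the titles in SAP Appendix 3 pair each endpoint's baseline with its change. Both point to the endpoint's own baseline, but the SAP text does not say so for the later endpoints.

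**The case against.** **The SD wording may be a slip for standard error.** The protocol is a translation, and the LS-mean code returns SEs. This is plausible. If so, the SD bars would never be drawn, but the phrase occurs twice and would be programmed as written, so it still needs correcting.

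**The harm is confined to display.** This stands. Model confidence limits are requested, and ANCOVA differences come with confidence intervals and p values. No inference changes.

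**The attrition cases are crude.** This also stands. SAP 3.4 maps withdrawal visits into the analysis windows (Week 4 is Days 22 to 32, with efficacy data counted up to 3 days after the last dose), so some subjects who stop early keep a Week 4 value. Discontinuations for other reasons are not counted. The result is not sensitive to this: the half-width ratio stays between about 4.1 and 4.6 in every case shown.

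**The covariate point is a preference.** Protocol and SAP agree on the model, nothing requires the CMH factors in these analyses, and the minimization factors are not given, so no allocation factor can be shown to have been left out. For EASI and BSA the endpoint's own baseline already carries severity information. The R² range is assumed, and the simulation covers a single-visit ANCOVA, not the MMRM. All of this limits the point to a possible improvement. It remains worth making because the data are already collected, the SAP itself uses these factors elsewhere, and the cost if they explain nothing is very small.

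**The own-baseline reading is already clear from context.** Largely so. It is a clarification only.

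**Conclusion.** The concern holds and is minor.

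- **Figures.** The error bars are wrong for their purpose as written. With 64 to 80 observed per arm they would be about 4.1 to 4.6 times as wide as a 95% confidence half-width. This rests on the simple-mean approximation; the 64 is an assumed 20% loss.
- **Model terms.** This is an available gain in precision, not an inconsistency between the documents. At an assumed partial R² of 1% to 10%, the SE falls by 0.5% to 5.3% if the factors are balanced across arms and by 0.1% to 4.9% if they fall at random. With no explanatory value, it is unchanged if balanced and 0.2% to 0.5% larger if random. There is no bias, and neither the primary test nor its type I error control is affected. EASI 75 and the other binary secondary endpoints are unaffected, because they use the stratified CMH test.
- **Baseline covariate.** The intended reading is recoverable from the protocol, but one explicit sentence would prevent a programming error.

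**What to change.** 1. In the figure sentences of SAP 8.2.2 and 8.2.4, replace the standard deviation with the 95% confidence interval (preferred, since it matches the primary figure) or the standard error, and label the bars in CF-2.1 and CF-2.2. Cost: wording and figure programming only. It can be made at any time.
2. In the MMRM and ANCOVA, add age group and baseline IGA for EASI, POEM and affected BSA, age group for IGA change, and baseline IGA for VRS. Cost: one or two degrees of freedom, an SE at most about 0.5% larger if the factors explain nothing, and an entry in SAP section 14, because Protocol 7.4.2 lists the model terms and section 14 now records only one unrelated change. If treatment codes have already been opened, present this as a supplementary analysis and keep the protocol model as planned.
3. In SAP 8.2.4 to 8.2.8, state that the baseline covariate is the baseline value of the endpoint being analysed. Cost: one sentence.
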